### **Inclusion/Exclusion Criteria**

Inclusion Criteria: A woman will be eligible for enrollment in this study only if all of the following inclusion criteria apply and have been met at the time of the Week 24/Baseline visit:

1. Completed 24 weeks of study drug treatment and study participation in either MVT-601-3101 or MVT-601-3102;
2. Has voluntarily signed and dated the informed consent form prior to initiation of any study-specific procedures for MVT-601-3103;  
Note: Procedures conducted as part of the parent study that also serve as baseline procedures for this study will be done under the informed consent for the parent study.
3. Is not expected to undergo gynecological surgery or other surgical procedures for treatment of endometriosis (including ablation, shaving, or excision) during the study, including during the Follow-Up Period, and the patient does not desire such treatment during this time frame;
4. Has a negative urine pregnancy test at the Week 24/Baseline visit;
5. Has agreed to continue to use only study-specified analgesic medications during the study and is not known to be intolerant to these;
6. Agrees to continue to use acceptable nonhormonal contraceptive methods as described in [Section 4.6](#) consistently during the Open-Label Treatment Period and for at least 30 days after the last dose of study drug. However, the patient is not required to use the specified nonhormonal contraceptive methods if she:
  - a. Has a sexual partner(s) who was vasectomized at least 6 months prior to the Week 24/Baseline visit;
  - b. Had a bilateral tubal occlusion (including ligation and blockage methods such as EssureTM), at least 6 months prior to the Week 24/Baseline visit (patients with Essure must have prior confirmation of tubal occlusion by hysterosalpingogram) and there must be no evidence of post-Essure syndrome;
  - c. Has a nonhormonal intrauterine device (eg, Paragard®) placed in the uterus;
  - d. Is not sexually active with men; periodic sexual relationship(s) with men requires the use of nonhormonal contraception as noted above;

- e. Practices total abstinence from sexual intercourse, as her preferred lifestyle; periodic abstinence is not acceptable.

**Exclusion Criteria:** None of the following criteria may be true for a patient to be eligible for enrollment into this study.

1. Has had a surgical procedure for treatment of endometriosis at any time during the parent study (MVT-601-3101 or MVT-601-3102);

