### **4.3. Selection of Study Population**

The study population will include approximately 800 premenopausal women aged 18 to 51 years with endometriosis-associated pain.

Deviations from inclusion and exclusion criteria are not allowed because they can potentially jeopardize the scientific integrity of the study, regulatory acceptability, or patient safety. Therefore, adherence to the criteria as specified in the protocol is essential. Any questions regarding patient eligibility and entry criteria should be discussed with the medical monitor.

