#### **4.3.1. Inclusion/Exclusion Criteria**

Inclusion Criteria (all inclusion criteria must have been met prior to randomization):

1. Completed 24 weeks of study drug treatment and study participation in either MVT-601-3101 or MVT-601-3102;
2. Has voluntarily signed and dated the informed consent form prior to initiation of any study-specific procedures for MVT-601-3103;

Note: Procedures conducted as part of the parent study that also serve as baseline procedures for this study will be done under the informed consent for the parent study.

3. Is not expected to undergo gynecological surgery or other surgical procedures for treatment of endometriosis (including ablation, shaving, or excision) during the study, including during the Follow-Up Period, and the patient does not desire such treatment during this time frame;
4. Has a negative urine pregnancy test at the Week 24/Baseline visit;
5. Has agreed to continue to use only study-specified analgesic medications during the study and is not known to be intolerant to these;
6. Agrees to continue to use acceptable nonhormonal contraceptive methods as described in [Section 4.6](#) consistently during the Open-Label Treatment Period and for at least 30 days after the last dose of study drug. However, the patient is not required to use the specified nonhormonal contraceptive methods if she:
  - a. Has a sexual partner(s) who was vasectomized at least 6 months prior to the Week 24/Baseline visit;
  - b. Had a bilateral tubal occlusion (including ligation and blockage methods such as Essure™), at least 6 months prior to the Week 24/Baseline visit (patients with Essure must have prior confirmation of tubal occlusion by hysterosalpingogram) and there must be no evidence of post-Essure syndrome;
  - c. Has a nonhormonal intrauterine device (eg, Paragard®) placed in the uterus;
  - d. Is not sexually active with men; periodic sexual relationship(s) with men requires the use of nonhormonal contraception as noted above;
  - e. Practices total abstinence from sexual intercourse, as her preferred lifestyle; periodic abstinence is not acceptable.

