#### Exclusion Criteria

1. Has had a surgical procedure for treatment of endometriosis at any time during the parent study (MVT-601-3101 or MVT-601-3102);
2. Has any chronic pain or frequently recurring pain condition, other than endometriosis, that is treated with opioids or requires analgesics for  $\geq 7$  days per month;
3. Has a weight that exceeds the weight limit of the DXA scanner or has a condition that precludes an adequate DXA measurement at the lumbar spine and proximal femur (eg, bilateral hip replacement, spinal hardware in the lumbar spine);
4. Has a Z-score  $< -2.0$  or has a  $\geq 7\%$  decrease in bone mineral density from the parent study Baseline at lumbar spine, total hip, or femoral neck based on the parent study Week 24 DXA assessment of bone mineral density;
5. Anticipated to use any prohibited medications as detailed in [Section 5.10.1](#);

6. Has any contraindication to treatment with low-dose estradiol and norethindrone acetate, including:
  - a. Known, suspected, or history of breast cancer;
  - b. Known or suspected estrogen-dependent neoplasia;
  - c. Active deep vein thrombosis or pulmonary embolism, or history of these conditions prior to the Week 24/Baseline visit;
  - d. History of or active arterial thromboembolic disease, including stroke and myocardial infarction;
  - e. Known anaphylactic reaction or angioedema or hypersensitivity to estradiol or norethindrone acetate;
  - f. Known protein C, protein S, or antithrombin deficiency, or other known thrombophilia disorders, including Factor V Leiden;
  - g. Migraine with aura;
  - h. History of porphyria;
7. Has current active liver disease from any cause;
8. Has a systemic autoimmune disease (eg, systemic lupus erythematosus, Sjogren's syndrome, rheumatoid arthritis, polymyositis, systemic sclerosis, psoriasis, psoriatic arthritis, vasculitic syndromes, etc); psoriasis not requiring or anticipated to require systemic therapy is permitted;
9. Had any of the following clinical laboratory abnormalities at the parent study Week 20 visit or, if available, any subsequent visit in one of the parent studies (MVT-601-3101 or MVT-601-3102):
  - a. Alanine aminotransferase (ALT) or aspartate aminotransferase (AST) > 2.0 times the upper limit of normal (ULN); or
  - b. Bilirubin (total bilirubin) > 1.5 x ULN (or > 2.0 x ULN if secondary to Gilbert syndrome or pattern consistent with Gilbert syndrome);

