#### **4.6. Contraception/Pregnancy Avoidance**

In this study, medications and devices containing hormones for contraception are excluded, and patients must agree to use nonhormonal contraception throughout the study including through 30 days following the last dose of study drug, unless any of the following apply:

- Has a sexual partner(s) who was vasectomized at least 6 months prior to the Week 24/Baseline visit;
- Had a bilateral tubal occlusion (including ligation and blockage methods such as Essure™) at least 6 months prior to the Week 24/Baseline visit (patients with Essure must have prior confirmation of tubal occlusion by hysterosalpingogram) and there must be no evidence of post-Essure syndrome;
- Has a nonhormonal intrauterine device (eg, Paragard®) placed in the uterus;
- Is not sexually active with men; periodic sexual relationship(s) with men requires the use of nonhormonal contraception as described below;
- Practices total abstinence from sexual intercourse, as her preferred lifestyle; periodic abstinence is not acceptable.

The only acceptable methods of contraception for those for whom one of the above methods do not apply are:

- Condom (male or female condom) with or without spermicide (cream, spray, foam, gel, suppository, or polymer film);
- Diaphragm with spermicide (condom may or may not be used);
- Cervical cap with spermicide (condom may or may not be used); or
- Vaginal sponge impregnated with spermicide used with a condom.

Patients will be provided with information on acceptable methods of contraception as part of the informed consent process and will confirm with signing of the consent form that they understand the requirements for avoidance of pregnancy during the course of the study. Patients may not donate ova during the course of the study and for 2 months following the last dose of study drug.

A patient may start hormonal contraception 4 weeks after her last study dose of study drug provided her menstrual cycle has returned.

Urine pregnancy tests will be performed at monthly intervals during the study (including just prior to receiving the first dose of study drug), and patients will receive continued guidance with respect to the avoidance of pregnancy as part of the study procedures. Patients who become pregnant during the study will be withdrawn from the study and followed for pregnancy outcome (see [Section 7.8](#)).

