## **5.10. Prior and Concomitant Medications and Non-Drug Therapies**

### **5.10.1. Prohibited Medications**

[Table 5-2](#) provides examples of prohibited drug categories; however, it is not a comprehensive list of all restricted medications. Drugs and drug classes in [Table 5-2](#) are prohibited at any time during the study through the Follow-Up visit, except as noted in the table. Consult the medical monitor if there is any uncertainty regarding patient use of a particular drug or drug class.

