**Table 5-2 Prohibited Medications**

Drug Class	Examples	Comments
Bisphosphonates	alendronate etidronate zoledronic acid	
GnRH analogues	leuprolide acetate injection, also known as leuprorelin goserelin acetate injection	
Anti-androgens	danazol	
Anticonvulsant drugs (specified)	phenobarbital carbamazepine phenytoin valproic acid primidone	Note: All other anticonvulsants are allowed
Aromatase inhibitors	anastrozole letrozole	
Progestins and progestin implants	dienogest norethindrone medroxyprogesterone cyproterone etonogestrel	
Estrogens	estradiol valerate conjugated estrogens ethynyl estradiol	
Hormonal contraceptives, contraceptive patches and vaginal rings	combined or progestin only NuvaRing	
Selective estrogen receptor modulators	raloxifene bazedoxifene lasofoxifene clomifene tamoxifen	
Selective progesterone receptor modulators	mifepristone ulipristal acetate	
Over-the-counter and herbal products/teas with known hormonal activity	plant-based estrogen products “natural” thyroid supplements dihydroepiandrosterone (DHEA)	
Intrauterine devices	levonorgestrel copper	

Drug Class	Examples	Comments
Bone agents	calcitonin calcitriol ipriflavone teriparatide denosumab abaloparatide odanacatib romosozumab	Calcium and Vitamin D2 and Vitamin D3 (ergocalciferol and cholecalciferol) are allowed without restriction.
Glucocorticoids	prednisolone or prednisone dexamethasone	Anticipated use of systemic glucocorticoids at an oral prednisone-equivalent dose of more than 5 mg every other day during the study.  Note: topical, inhaled, intranasal, otic, ophthalmic, intraarticular, or intralesional subcutaneous are permitted without restriction.  Short duration (< 21 days) higher-dose glucocorticoids required for acute events are permitted during the study.
P-glycoprotein inducers	avasimibe carbamazepine phenytoin rifampin St. John's wort tipranavir/ritonavir f	Note: For patients requiring a short course of these drugs during the study, investigator must contact the medical monitor for approval and guidance on study drug administration during this period.

Drug Class	Examples	Comments

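### Table 5-2 prohibits copper intrauterine devices without exception, while inclusion criterion 6c and Section 4.6 accept nonhormonal ones (original protocol and Amendment 1)

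*Protocol*

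**What the plan says.** The relevant text is the same in the original protocol and in Amendment 1, apart from section numbers.

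- **Inclusion criterion 6c** (synopsis and Section 4.3.1) exempts a woman from the specified nonhormonal contraceptive methods if she "Has a nonhormonal intrauterine device (eg, Paragard®) placed in the uterus".
- **Section 4.6** repeats that exemption and states what is ruled out: "medications and devices containing hormones for contraception are excluded".
- **Table 5-2** (Section 5.9.1 in the original, 5.10.1 in Amendment 1) has a row for intrauterine devices. Its examples are "levonorgestrel copper" and its comments cell is empty.
- **The text introducing Table 5-2** says that the listed drugs and drug classes "are prohibited at any time during the study through the Follow-Up visit, except as noted in the table".
- **Exclusion criterion 5** reads "Anticipated to use any prohibited medications as detailed in" that same section, and the synopsis says of the exclusion criteria: "None of the following criteria may be true for a patient to be eligible for enrollment".
- **Section 4.3** permits no deviations from the entry criteria and adds: "Any questions regarding patient eligibility and entry criteria should be discussed with the medical monitor".

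**The concern.** The same device is accepted by one entry rule and prohibited by another. If Table 5-2 and exclusion criterion 5 are applied as written, the exemption in 6c has no effect, because any woman who uses it fails an exclusion criterion.

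Sites could then act differently. One that follows the table would turn away a woman whose contraception the protocol accepts. One that follows 6c and Section 4.6 would enrol her and might then record an eligibility or prohibited-therapy deviation that is not a real one. The table also applies throughout treatment and follow-up, so the conflict continues after enrolment. Contraception is the eligibility measure that Table 7-2 gives against reproductive toxicity, so sites need a single answer on which methods are acceptable.

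**Working it through.** No arithmetic beyond counting applies. The check compares the relevant sections within each version.

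**Step 1: where each position is stated**

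| Version | Nonhormonal device accepted | Copper device prohibited |
|---|---|---|
| Original protocol | Synopsis 6c; Section 4.3.1, 6c; Section 4.6 (3 places) | Table 5-2, Section 5.9.1 (1 place) |
| Amendment 1 | Synopsis 6c; Section 4.3.1, 6c; Section 4.6 (3 places) | Table 5-2, Section 5.10.1 (1 place) |

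**Step 2: does the table contain an exception?** The introductory text recognises only exceptions noted in the table. In Amendment 1 the table has 18 drug-class rows, of which 7 carry a comment: anticonvulsants, bone agents, glucocorticoids, P-glycoprotein inducers, P-glycoprotein inhibitors, analgesics and antidepressants. That leaves 18 − 7 = 11 rows without one, including intrauterine devices. Where the authors meant to narrow a prohibition they wrote it in; the anticonvulsant row, for example, says "Note: All other anticonvulsants are allowed". The device row has no comment in either version.

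**Step 3: does the prohibition reach eligibility?** Exclusion criterion 5 points to the section that holds Table 5-2. No exclusion criterion may be true for an enrolled patient, and Section 4.3 allows no deviations. The table entry is therefore an entry bar as well as a rule for conduct on study.

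**Step 4: does the conflict depend on outside knowledge of the named product?** No. The row prohibits the whole class of intrauterine devices and names copper, so a nonhormonal device accepted under 6c falls in the prohibited class whatever the named product is made of.

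**Step 5: is this only a difference between versions?** No. The conflict is present inside each version. The Amendment 1 summary of changes lists no change to 6c or to the device row, although that amendment did revise the contraception wording in Section 4.6 and add a footnote to Table 5-2.

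**The case against.** The strongest objection concerns currency. The document lists Amendments 2, 3 and 3.1, and the text shown stops in the synopsis of a later version that runs to Week 104. The entry criteria and Table 5-2 of that version are not visible, so the row may already have been corrected. This stands as a limit: the finding is established for the original protocol and Amendment 1 only.

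The second objection is that the intent is plain. Section 4.6 is the dedicated contraception section and rules out only hormone-containing products, and acceptance is repeated while prohibition rests on one word in a table of examples. That is a fair guide to what was meant, and it determines the direction of the correction. It does not remove the conflict, because the protocol gives no rule of precedence and the table is itself specific in naming copper.

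Third, exclusion criterion 5 speaks of medications, and a copper device is not a medication. But the criterion refers to a section whose table lists intrauterine devices as a prohibited class, so the literal reading is fair.

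Fourth, sites are told to take uncertainty to the medical monitor. This makes divergence possible rather than certain. It settles single cases, and only where a site notices the conflict.

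Finally, every entrant has just completed 24 weeks in a parent study and agrees to continue acceptable contraception. Whether a device user could first be refused here depends partly on parent-protocol rules that are not shown. The number of women affected may well be small.

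**Conclusion.** The concern holds for the original protocol and Amendment 1. In each, a contraceptive method accepted in three places is prohibited in a fourth, with no exception noted, and exclusion criterion 5 turns that prohibition into an entry bar. This is an operative rule stated wrongly, judged by the protocol's own contraception section.

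The impact is low. The number of women concerned is unknown, since the documents give no count of device users. No endpoint, estimate, analysis set or error rate changes. The possible harm is a wrongly refused patient or a spurious deviation.

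The conclusion rests on reading the table and exclusion criterion 5 literally. Whether correction is still needed depends on the later amendments, which cannot be checked here.

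**What to change.** Bring Table 5-2 into line with Section 4.6. Either delete copper and limit the row to hormonal (levonorgestrel) devices, or add a comment that nonhormonal intrauterine devices are allowed. Exclusion criterion 5, inclusion criterion 6c and Section 4.6 then need no change. Notify sites so that all apply the same rule.

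The cost is one word deleted or one table comment added at the next amendment, plus the notification. First check Table 5-2 in the governing version; if the row has already been corrected, no action is required.

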#### Exclusion Criteria

1. Has had a surgical procedure for treatment of endometriosis at any time during the parent study (MVT-601-3101 or MVT-601-3102);
2. Has any chronic pain or frequently recurring pain condition, other than endometriosis, that is treated with opioids or requires analgesics for  $\geq 7$  days per month;
3. Has a weight that exceeds the weight limit of the DXA scanner or has a condition that precludes an adequate DXA measurement at the lumbar spine and proximal femur (eg, bilateral hip replacement, spinal hardware in the lumbar spine);
4. Has a Z-score  $< -2.0$  or has a  $\geq 7\%$  decrease in bone mineral density from the parent study Baseline at lumbar spine, total hip, or femoral neck based on the parent study Week 24 DXA assessment of bone mineral density;
5. Anticipated to use any prohibited medications as detailed in [Section 5.10.1](#);

6. Has any contraindication to treatment with low-dose estradiol and norethindrone acetate, including:
  - a. Known, suspected, or history of breast cancer;
  - b. Known or suspected estrogen-dependent neoplasia;
  - c. Active deep vein thrombosis or pulmonary embolism, or history of these conditions prior to the Week 24/Baseline visit;
  - d. History of or active arterial thromboembolic disease, including stroke and myocardial infarction;
  - e. Known anaphylactic reaction or angioedema or hypersensitivity to estradiol or norethindrone acetate;
  - f. Known protein C, protein S, or antithrombin deficiency, or other known thrombophilia disorders, including Factor V Leiden;
  - g. Migraine with aura;
  - h. History of porphyria;
7. Has current active liver disease from any cause;
8. Has a systemic autoimmune disease (eg, systemic lupus erythematosus, Sjogren's syndrome, rheumatoid arthritis, polymyositis, systemic sclerosis, psoriasis, psoriatic arthritis, vasculitic syndromes, etc); psoriasis not requiring or anticipated to require systemic therapy is permitted;
9. Had any of the following clinical laboratory abnormalities at the parent study Week 20 visit or, if available, any subsequent visit in one of the parent studies (MVT-601-3101 or MVT-601-3102):
  - a. Alanine aminotransferase (ALT) or aspartate aminotransferase (AST) > 2.0 times the upper limit of normal (ULN); or
  - b. Bilirubin (total bilirubin) > 1.5 x ULN (or > 2.0 x ULN if secondary to Gilbert syndrome or pattern consistent with Gilbert syndrome);
10. Is currently pregnant or lactating, or intends to become pregnant during the study period or within 1 month after the last dose of study drug, or plans to donate ova during the study period or within 2 months after the last dose of study drug;
11. The presenting visual acuity score has decreased by 10 or more points at the Week 24/Baseline visit relative to the parent study Baseline visit;  
Note: Visual acuity score must have been obtained with corrective lenses, if applicable.
12. Is inappropriate for participation in this study because of conditions that may interfere with interpretation of study results or prevent the patient from complying with study requirements, as determined by the investigator, sub-investigator, or medical monitor;
13. Met a withdrawal criterion in the parent study (MVT-601-3101 or MVT-601-3102).

#### **4.4. Method of Assigning Patients to Treatment Group and Patient Identification Number**

Eligible patients who sign consent will be identified with the same Patient Identification (ID) Number assigned to the patient during the parent study. This extension study is a single-arm

study, and thus all eligible patients are assigned to the same treatment group of relugolix 40 mg co-administered with low-dose of estradiol and norethindrone acetate (see [Section 5.1](#) for treatment details).

#### 4.5. Removal of Patients from Therapy

Completion of the Week 52 visit defines completion of the study. Patients may withdraw consent to participate in the study and discontinue treatment at any time for any reason. Investigators or the medical monitor may remove patients from therapy under this protocol for reasons of safety and/or lack of compliance as discussed below. Patients removed from therapy for any reason will undergo the assessments for the Early Termination visit (see the Week 52 visit on the Schedule of Activities, [Section 1.1](#)) and will have a Follow-up visit to assess safety approximately 30 days after the end of study drug treatment (ie, after the patient's last dose of study medication). When patients complete the study or early terminate from the study, they must be deactivated from the study in the IVRS/IWRS, eDiary, and tablet device.

The following safety and/or compliance events will result in the removal of patients from therapy either permanently or until the etiology of the problem has been identified and resolved:

- Any adverse event that is intolerable to the patient and that cannot be ameliorated by the use of adequate medical intervention, or that in the opinion of the investigator or medical monitor would lead to undue risk to the patient if dosing continued;
- If it is discovered after enrollment that a patient failed to meet protocol entry criteria and continued participation poses an unacceptable risk to the patient's health;
- If the following liver test abnormalities develop, study drug should be discontinued immediately with appropriate clinical follow-up (including repeat laboratory tests, until a patient's laboratory profile has returned to normal/baseline status):
  - ALT or AST > 8 x ULN; or
  - ALT or AST > 5 x ULN and persists for more than 2 weeks; or
  - ALT or AST > 3 x ULN in conjunction with elevated total bilirubin > 2 x ULN or international normalized ratio (INR) > 1.5; or
  - ALT or AST > 3 x ULN with appearance of fatigue, nausea, vomiting, right upper quadrant pain or tenderness, fever, rash and/or eosinophilia (> 5%);
- QT interval by the Fridericia correction (QTcF) prolongation of more than 500 msec read by a cardiologist;
- Evidence of endometrial hyperplasia or endometrial carcinoma on endometrial biopsy;
- If the patient has a  $\geq 7\%$  loss of bone mineral density at lumbar spine, total hip, or femoral neck compared with the parent study Baseline;
- If the patient, in the opinion of the investigator or the medical monitor, is grossly noncompliant with the protocol's requirements. Gross noncompliance includes < 75% compliance with the study drug over > 2 consecutive months; missing multiple study visits; and persistent (> 2 consecutive months) with < 50% of the required number of days of eDiary completion. Investigators will follow up with the patient and encourage compliance with study drug or eDiary prior to discontinuing her from the study;

- If the patient becomes pregnant at any time after providing a signed informed consent form, the patient must be withdrawn immediately (see [Section 7.8](#) for information on pregnancy reporting).

Should a patient fail to attend the clinic for a required study visit within the protocol-defined window, the site should attempt to contact the patient and reschedule the missed visit as soon as possible. The site should also counsel the patient on the importance of maintaining the assigned visit schedule and determine whether the patient can and/or should continue in the study based on previous noncompliance. In cases where the patient does not return for the rescheduled visit or cannot be reached to reschedule the missed visit, the site should make every effort to regain contact with the patient. The site should attempt at least three documented telephone calls and if necessary a certified letter to the patient's last known mailing address so that they can appropriately be withdrawn from the study with a primary reason of "Lost to Follow-up."

